11.3. Adverse Events / Adverse Drug Reactions

Adverse events (AEs), which include abnormal and clinically significant clinical laboratory test variables, will be monitored and documented from the time of Informed Consent until study participation is complete (the Follow-up Visit).

All AEs will be coded using Medical Dictionary for Regulatory Activities (MedDRA) version 22.0. The focus of the analysis will be on TEAEs, which will in general be summarized by treatment group and for the combined BPN14770 groups using preferred term (PT) and primary system organ class (SOC). Pre-treatment AEs will be listed (along with all the TEAEs, in the same listing), sorted by start day/date, but pre-treatment AEs will not be tabulated.

TEAEs are defined as any AE that start on or after the first dose of the study drug, or any event that is present at baseline, continues after the first dose of the study drug, and worsens in severity or in frequency. See Section 9.2.3 of the protocol for definition of serious adverse events (SAEs).

Adverse events with incomplete start dates will be considered a TEAE if:

- Day and month are missing and the year is equal to or after the year of the first dose date;
- Day is missing and the year is after the year of the first dose;
- Day is missing and the year is equal to the year of the first dose date and the month is equal to or after the month of the first dose date
- Year is missing; or
- Entire date is missing.

If the relationship to study treatment or the severity (intensity) of the AE is missing, these will be left as missing, and the event will not be included in the tabulations for relatedness and intensity.

For summaries by SOC and PT, a subject will be counted once at the SOC level and once at each PT within the SOC level. For summaries by SOC, PT, and maximum severity, a subject will be counted once at the highest severity level for which the event occurred at the SOC level and the highest severity level for each unique PT within that SOC level. Subjects will be counted only once within each SOC and PT at the strongest relationship to study drug in the following order: Related (possibly related, probably related, or related); Not Related (defined as unlikely related, unrelated, not related, no relation) to study drug.

The summaries presenting frequency of TEAEs will be ordered by decreasing frequency of the combined BPN14770 groups by SOC and PT.

Summary tables of TEAEs will summarize the number and percentage of subjects for the following:

This document is confidential.

- An overall summary of the number and percentage of subjects reporting TEAEs, study drug-related TEAEs, severe TEAEs, serious TEAEs, TEAEs leading to study drug discontinuation, and TEAEs leading to death.
- TEAEs overall and by SOC and PT
- Study drug-related TEAEs overall and by SOC and PT
- TEAEs by maximum relationship to study treatment, overall and by SOC and PT
- TEAEs by maximum severity, overall and by SOC and PT
- Serious TEAEs, overall and by SOC and PT
- TEAEs leading to study drug discontinuation, overall and SOC and PT

Only TEAEs will be included in the summary tables, but all AEs will be listed. Separate listings for SAEs, TEAEs leading to study drug discontinuation, and TEAEs leading to death will also be provided . A separate listing of death events will also be provided. All AE listings will include Study Day (start and stop) for the start dates and stop dates and will be sorted by Start Day.

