9 EVALUATION AND REPORTING OF ADVERSE EVENTS

9.1 Adverse Events

An adverse event is defined as any untoward medical occurrence in a clinical investigation subject administered a pharmaceutical product, which does not necessarily have a causal relationship with this treatment. An adverse event can therefore be any unfavorable and/or unintended sign (including an abnormal laboratory finding), symptom, or disease temporally associated with the use of an investigational medicinal product, whether or not related to the investigational medicinal product. All adverse events, including observed or volunteered problems, complaints, or symptoms, are to be recorded on the appropriate eCRF.

Adverse events, which include abnormal and clinically significant clinical laboratory test variables, will be monitored and documented from the time Informed Consent until study participation is complete (the Follow-up Visit). Subjects should be instructed to report any adverse event that they experience to the Investigator. Any medical condition present prior to consent should be recorded in medical history. Beginning with the signing of the informed consent until the time of the first dose of study drug, investigators should make updates to source records to document any pre-existing medical condition or signs or symptoms that change in severity, frequency, or seriousness in the medical history; if the subject is subsequently randomized, these occurrences will be reported as adverse events that began prior to dosing. Serious adverse events that occur prior to the first dose of study drug should be reported similarly, except that an SAE report will be completed regardless of whether the subject is randomized.

Beginning with the first dose of study drug, investigators should make an assessment for adverse events at each visit and record all adverse events, non-serious and serious, on the appropriate adverse event eCRF.

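### SAP 11.3's partial-date rule ignores the stop date, so an adverse event known to have ended before first dose can be tabulated as treatment-emergent

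*SAP*

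**What the plan says.** SAP 11.3 defines a TEAE by two routes. The first is onset: "TEAEs are defined as any AE that start on or after the first dose of the study drug". The second is worsening of something already there: "any event that is present at baseline, continues after the first dose of the study drug, and worsens in severity or in frequency". Pre-treatment events are to be listed, but "pre-treatment AEs will not be tabulated".

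The section then handles incomplete dates: "Adverse events with incomplete start dates will be considered a TEAE if" any one of five conditions holds. Three of them matter most here:

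- Only the start year was recorded, and it matches the first-dose year or comes later.
- The start month and year were recorded without a day: "Day is missing and the year is equal to the year of the first dose date and the month is equal to or after" (the comparison is with the month of dosing).
- No part of the start date was recorded at all.

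The other two are a missing year, and a missing day with a year later than that of first dose. Neither the list nor the rest of SAP 11.3 makes the stop date a condition on TEAE status.

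Pre-dose events can be in the data. SAP 11.3 and Protocol 9.1 both document adverse events from informed consent. Protocol 10.2 allows a screening period of up to 28 days, longer if washout is needed. For pre-existing conditions, signs or symptoms that change between consent and first dose, Protocol 9.1 says that in subjects later randomized "these occurrences will be reported as adverse events that began prior to dosing". Stop dates are also available, because SAP 11.3 puts start and stop study days in every adverse event listing.

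**The concern.** Treating an event as treatment-emergent when its timing is unknown is ordinary safety practice. The difficulty is that this rule also applies when the timing is known. If the stop date falls before first dose, the event is over before any drug is taken, however little is recorded about its start. It meets neither route of the definition, yet a programmer who follows the list literally will flag it as a TEAE.

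TEAEs are the main safety output, and only TEAEs enter the summary tables. The stake is a slight overstatement of TEAE incidence, from events that cannot be effects of study drug, and a derivation that disagrees with the SAP's own definition.

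**Working it through.** The plan gives no figure to reproduce, so the check is one of logic, followed by an illustration of the rule's reach.

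**1. Rule against definition.** The five conditions were applied as written to invented events, with first dose on 20 March 2019.

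| Recorded start | Recorded stop | Partial-date rule | Definition | Rule with a stop-date check |
|---|---|---|---|---|
| March 2019, day missing | 10 March 2019 | TEAE | not TEAE | not TEAE |
| 2019, day and month missing | 1 March 2019 | TEAE | not TEAE | not TEAE |
| wholly missing | 10 March 2019 | TEAE | not TEAE | not TEAE |
| February 2019, day missing | 10 March 2019 | not TEAE | not TEAE | not TEAE |

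The rule and the definition disagree in the first three rows. A stop-date check removes each disagreement. An event with no stop date, or with a stop date on or after first dose, is classified as before.

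**2. Comparison within the SAP.** SAP 7.4 uses the same five conditions for medications but applies them to the end date, which shows whether a drug was still being taken at dosing. SAP 11.3 applies them to the start date and has no end-date step.

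**3. Reach when only the day is missing (illustration).** Assumptions: first dose on each of the 365 days of one year, and onset uniform over a stated range of days before dosing. The rule flags the event when onset falls in the calendar month of first dose.

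- Onset 1 to 28 days before dosing: 365 × 28 = 10,220 combinations, of which 5,348 share the month; 5,348 / 10,220 = 52%.
- Onset 8 to 28 days before: 365 × 21 = 7,665 combinations, of which 3,129 share the month; 3,129 / 7,665 = 41%.
- Onset 15 to 28 days before: 365 × 14 = 5,110 combinations, of which 1,498 share the month; 1,498 / 5,110 = 29%.

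The second and third lines are more relevant, because an event that also resolves before dosing tends to have started earlier. With the year or the whole date missing, the rule flags every event by construction. That is the least plausible gap for an event a few weeks old.

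**4. Size per subject.** In an arm of 85, one wrongly counted subject adds 1/85 = 1.2 percentage points. This is a maximum. SAP 11.3 counts a subject once per system organ class and once per preferred term, so a subject who already has a qualifying event there adds nothing.

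**5. Effect on the comparison between arms.** Suppose a share q of the subjects not yet counted is wrongly added in every arm. A true incidence p becomes p + q(1 − p), and the risk difference is multiplied by (1 − q). With q = 1/85:

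- A 10-point difference becomes 10 × 84/85 = 9.88 points.
- Incidences of 30% and 20% become 30.8% and 20.9%, and the ratio moves from 1.50 to 1.47.

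**The case against.** The strongest reply is that the affected set is very narrow. The event must arise before dosing, resolve before dosing, lack part of its start date, and still have a stop date good enough to place its end before first dose. Protocol 12.1 and 12.5 have missing data queried and accounted for, which should leave few incomplete dates. Some pre-dose findings may never become adverse events. The Schedule of Assessments starts adverse event recording at Baseline, and Protocol 8.4 sends examination changes between Screening and Baseline to medical history. Any misclassified event would also be visible in the listings, which carry stop dates. All of this stands, and it limits the size of the problem. It does not remove the contradiction, because SAP 11.3 itself expects pre-treatment events and plans to list them.

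A second reply is that defaulting to TEAE is deliberately conservative. That is right where timing is unknown, and the proposed change keeps the default there. It is no defence where the stop date settles the matter.

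A reader might go further and infer that the rule biases the comparison of active arms with placebo, or materially dilutes it. The documents do not support that. Pre-dose events cannot depend on the randomized arm, the rule is identical in all arms, and one extra subject per arm barely moves the comparison unless the event is rare. Nor should the 52% be read as the share of pre-treatment events that will be tabulated. It applies only to events with a missing start day, ignores the need to resolve before dosing, and has an unknown and possibly empty denominator.

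**Conclusion.** The rule is wrong as written. As stated, it classes as treatment-emergent some events that the definition in the same section excludes. The finding is confined to events with an incomplete start date whose stop date shows that they ended before first dose. Events with complete start dates are unaffected.

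The likely effect is a slight rise in TEAE incidence, at most 1.2 percentage points per affected subject in an arm of 85. The documents give no count of such events, so the total cannot be sized, though it is probably very small. The shares of 52%, 41% and 29% illustrate reach under assumed uniform onset and are not forecasts. Nothing shows that a conclusion of the trial is at risk. This is a low-priority correction, worth making because it is clear-cut.

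**What to change.** Add to the partial-date list in SAP 11.3: *An event with an incomplete start date is not a TEAE if its stop date (complete or partial) shows that it ended before the first dose of study drug.* Keep the conservative default for all other events with incomplete start dates, including those with no usable stop date.

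The cost is one sentence in the SAP and one condition in the adverse event derivation. No new data are needed, because stop dates are already carried in the listings.

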14.2.4. Body of the Data Display

14.2.4.1. *General Conventions*

Data in columns of a table or listing are formatted as follows:

- Alphanumeric values are left-justified;
- Whole numbers (eg, counts) are right-justified; and
- Numbers containing fractional portions are decimal aligned.

14.2.4.2. *Table Conventions*

- Units will be included where available
- If the categories of a parameter are ordered, then all categories between the maximum and minimum category are presented in the table, even if n=0 for all treatment groups in a given category that is between the minimum and maximum level for that parameter. For example, the frequency distribution for symptom severity would appear as:

Severity Rating	N
severe	0
moderate	8
mild	3

Where percentages are presented in these tables, zero percentages will not be presented and so counts of 0 will be presented as 0 and not as 0 (0%).

- If the categories are not ordered (eg, Medical History, Reasons for Discontinuation from the Study), then only those categories for which there is at least 1 subject represented in 1 or more groups are included.
- An Unknown or Missing category is added to each parameter for which information is not available for 1 or more subjects.

This document is confidential.

- Unless otherwise specified, the estimated mean and median for a set of values are printed out to 1 more significant digit than the original values, and standard deviations are printed out to 2 more significant digits than the original values. The minimum and maximum should report the same significant digits as the original values. For example, for systolic blood pressure:

n	XX
Mean (SD)	XXX.X (XXX.XX)
Median	XXX.X
Min, Max	XXX, XXX

- P-values are output in the format: "0.xxx", where xxx is the value rounded to 3 decimal places. Every p-value less than 0.001 will be presented as <0.001. If the p-value are less than 0.0001, then present as <0.0001. If the p-value is returned as >0.999, then present as >0.999

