- Percentage values are printed to one decimal place, in parentheses with no spaces, one space after the count (eg, 7 (12.8%), 13 (5.4%)). Values that round down to 0.0. will be displayed as '<0.1', or as appropriate with additional decimal places. Unless otherwise noted, for all percentages, the number of subjects in the analysis set for the treatment group who have an observation will be the denominator. Percentages after zero counts should not be displayed and percentages equating to 100% are presented as 100%, without decimal places.
- Tabular display of data for medical history, prior/concomitant medications, and all tabular displays of adverse event data are presented by the body system, treatment class, or SOC with the highest occurrence in the active treatment group in decreasing order, assuming all terms are coded. Within the body system, drug class and SOC, medical history (by preferred term), drugs (by ATC1 code), and adverse events (by preferred term) are displayed in decreasing order. If incidence for more than 1 term is identical, they should then be sorted alphabetically. Missing descriptive statistics or p-values which cannot be estimated are reported as "-".

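### SAP 11.3 drops adverse events with missing severity or causality from the severity and relatedness tables, against the SAP's own missing-category convention; this may understate related and severe counts and hides how much is missing

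*SAP*

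**What the plan says.** SAP 11.3 sets the rule for a TEAE whose relationship to treatment or severity is missing: "these will be left as missing, and the event will not be included in the tabulations for relatedness and intensity".

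The outputs that use these attributes are listed later in 11.3:
- "An overall summary of the number and percentage of subjects reporting TEAEs, study drug-related TEAEs, severe TEAEs, serious TEAEs", and further categories;
- "Study drug-related TEAEs overall and by SOC and PT";
- TEAEs by maximum relationship;
- "TEAEs by maximum severity, overall and by SOC and PT".

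In the by-SOC and by-PT tables a subject is counted once, at the highest severity or the strongest relationship.

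SAP 14.2.4.2 (Table Conventions) gives a general rule: "An Unknown or Missing category is added to each parameter for which information is not available for 1 or more subjects". That bullet has no exception clause, although other bullets in the same list open with one.

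For incomplete start dates, 11.3 takes the cautious course. The rule begins "Adverse events with incomplete start dates will be considered a TEAE if", and its last condition is that the whole date is missing.

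**The concern.** The two instructions produce different tables from the same data, and nothing in the SAP ranks them, so two programmers could each follow the SAP and disagree.

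The rule in 11.3 also works one way on an arm's own counts. A TEAE that is dropped cannot add a subject to the related or severe rows, but its absence can remove one. The reader of the table is not told how many events were set aside. Within the same section, an unknown start date is resolved toward counting the event as treatment-emergent, while an unknown grade or causality is resolved toward not counting it.

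Safety and tolerability of both doses against placebo is a stated objective (SAP 3.1), and the same section says the results will determine the Phase 3 dose or doses. The related and severe rows are a natural place to look when comparing tolerability of 10 mg and 25 mg.

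**Working it through.** The documents state no figure on this point, so there is nothing to reproduce. The check compares the rules and then bounds the effect.

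**Step 1. What each rule does to a TEAE with no severity grade**

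| | SAP 11.3 | SAP 14.2.4.2 |
|---|---|---|
| All-TEAE table by SOC and PT | kept | kept |
| Maximum-severity table | left out | shown in a Missing row |
| Count of severe TEAEs | not counted | not counted |
| Amount missing visible in the table | no | yes |

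The rules differ in what is displayed, but neither adds to the severe count.

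**Step 2. Direction within an arm.** A subject enters the severe row if at least one retained event is severe. Removing events from that set can only leave the subject's status unchanged or take the subject out of the row. The same holds for related. So the count may be too low and cannot be too high.

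**Step 3. When the effect cannot be seen in the totals.** Take a subject with one mild headache and a second headache with no grade. Under 11.3 the subject appears as mild, and the row totals still agree with the all-TEAE table. The same happens with one unrelated event and one with no causality entry. Only the listings would show it.

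**Step 4. The literal wording.** The trigger is that relationship *or* severity is missing. The exclusion is from the tabulations for relatedness *and* intensity. An event graded severe, with causality blank, therefore leaves the severity table as well. In that case the loss does not depend on guessing an unknown grade.

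**Step 5. Size.** Inputs:
- N = 85 per arm (SAP 3.4);
- s = 4 subjects with a known severe TEAE (assumption);
- m = 0 to 5 subjects per arm who have only an ungraded TEAE (assumption).

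Formulas: dropped = s/N; Missing row = m/N; upper bound, if every ungraded event were severe = (s + m)/N.

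| m | Severe, events dropped | Severe, with Missing row | Missing row | Upper bound |
|---|---|---|---|---|
| 0 | 4/85 = 4.71% | 4.71% | 0% | 4.71% |
| 1 | 4.71% | 4.71% | 1/85 = 1.18% | 5/85 = 5.88% |
| 3 | 4.71% | 4.71% | 3/85 = 3.53% | 7/85 = 8.24% |
| 5 | 4.71% | 4.71% | 5/85 = 5.88% | 9/85 = 10.59% |

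The largest shift per affected subject is 1/85 = 1.18 percentage points.

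For Step 4, suppose one of the four known severe subjects has a single severe event with causality blank. The reported rate becomes 3/85 = 3.53% instead of 4.71%, again a difference of 1.18 points.

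**Step 6. Denominator.** By default in 14.2.4.2, "the number of subjects in the analysis set for the treatment group who have an observation will be the denominator". If that were read as removing subjects with a missing grade, the percentage after dropping would rise slightly: 4/84 = 4.76% for m = 1 and 4/80 = 5.00% for m = 5. The one-way statement in Step 2 is therefore about subject counts.

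**The case against.** The case on the other side is substantial.

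- **Little may be missing.** The investigator assesses relationship and grades every event (Protocol 9.3.1 and 9.3.2). Missing data are queried with the site (Protocol 12.5). An eCRF is complete only once missing items are accounted for (Protocol 12.1). This stands, and it is why the harm is conditional.
- **The events are not lost.** They remain in the all-TEAE table and, where they qualify, in the serious and discontinuation tables. They are also in the listings: "Only TEAEs will be included in the summary tables, but all AEs will be listed". The Fisher's exact test in Protocol 11.5 compares AE incidence and is not specified by grade or causality. This stands too.
- **A specific rule may override a general one.** 11.3 is written for adverse events, and 14.2.4.2 is a layout convention worded in terms of subjects. That reading is reasonable, but the SAP does not state it, and it does not resolve the *or*/*and* problem in 11.3.
- **Counting missing causality as related is a choice.** Nothing in the documents requires it. This is correct; it is recommended as the cautious option, in keeping with how 11.3 treats start dates.

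A reader might infer three stronger things that the documents do not support. First, that related and severe events *are* understated: this needs values still missing at lock, events that belong in those categories (or, under the literal wording, a known severe event with causality blank), and subjects not already counted there. None of this is shown. Second, that the rule favours the drug: it applies to all arms under blinding, and a dropped placebo event makes the drug look relatively worse. Third, that the tables will not add up: subjects are counted at their maximum, so totals change only when a subject has no other classifiable event in that row.

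**Conclusion.** The conflict between 11.3 and 14.2.4.2 is real and unresolved in the text. The rule in 11.3 may understate, and can never overstate, the number of subjects per arm with related or severe TEAEs, and it conceals the extent of missing data. As worded, it would also take a known severe event out of the severity table because its causality field is blank.

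The size is unknown. It is zero if nothing is missing after queries, and otherwise at most 1.2 percentage points per affected subject, taking about 85 subjects per arm as the denominator. The assumed range of 0 to 5 affected subjects per arm would give a possible shortfall of 0 to 5.9 points; that range is illustrative and does not come from the documents. Nothing can be said about the direction of an effect on the active-versus-placebo comparison.

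This is a minor point. It leaves the efficacy analysis and overall TEAE incidence untouched, and is worth correcting because the correction is cheap.

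**What to change.** Replace the sentence in SAP 11.3 with a rule that says:

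1. A missing attribute affects only the tables for that attribute. An event with a known grade stays in the severity tables whatever its causality field holds, and the reverse.
2. TEAEs with missing relationship are counted as related, with the number so assigned given in a footnote. Say that this takes the place of the Missing category of 14.2.4.2 for relationship.
3. TEAEs with missing severity appear in a Missing row, as 14.2.4.2 requires. A subject who also has a graded event in that SOC or PT row is shown at the highest known grade and flagged.
4. All such events are flagged in the listings.

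The cost is SAP wording and minor programming. Related counts may be slightly less favourable, since some events counted as related may not be. The Missing row makes the severity gap visible but leaves the severe count as it is. If no values are missing at lock, no table changes.
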